Physiological factors of interest include: systemic inflammation, quadriceps strength, recruitment and fatigue, quadriceps function and dimension after rehabilitation. Psychological factors include: self-efficacy, anxiety, depression. Clinical factors include: adherence to the 12-week program, adherence to follow-up and number and severity of exacerbations.

COVID Patients

Objective 1. To determine the efficacy of a 12-week, home-based, patient-tailored, RAS-enhanced music exercise program and strength training in improving functional and clinical parameters in patients recovering from COVID19 with a history of an emergency room and/or hospital admission..

Hypotheses: Compared to patients randomized to a home-based, exercise program without music (control group), patients randomized to a home-based, exercise program augmented with RAST-therapeutic enhanced music (experimental group; hereafter referred to as RAST-music group) will demonstrate greater:

1a- increase in 6-minute walking distance (primary hypothesis);

1b- greater increases in rectus femoris dimensions (ultrasound)

1c- greater quadriceps force and endurance (magnetic femoral nerve stimulation; isokinetic strength testing)

1d- increased sense of emotional investment related to the music experience

Objective 2. To determine whether at 12 weeks the RAS-music group will accumulate a greater volume of daily physical activity than the control group. (same as COPD group)

Hypothesis: The RAST-music group will accumulate a greater volume of daily physical activity than the control group. This will be demonstrated by greater physical activity at 12 weeks (actigraphy).

Objective 3. To determine whether 24-weeks after randomization, gains in 6-minute walk distance and perceived functional improvements will be sustained to a greater extent in the RAST-music group

than in the control group (same as COPD group) and whether there is any change in 6-minute walk distance and perceived functional improvements in the control group.

Hypothesis: The RAST-music group will maintain improvements in measured and perceived function at 24 weeks to a greater extent than the control group. (same as COPD)

Objective 4. *To assess impact of physiological and psychological phenotype and clinical factors including those related to music preference and history on responsiveness to rehabilitation achieved with and without concurrent use of RAST music programs (Exploratory objective).*

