Specific physiological, psychological and clinical factors will include, quadriceps function and dimension after rehabilitation, self-efficacy, anxiety, depression, time of mechanical ventilation, *music preference and history*, and adherence to the program.

A.2. Impact: Using RAS-enhanced music to cue walking cadence and decrease exercise-induced dyspnea/fatigue has the potential to transform home-based pulmonary rehab. Altering the beat and tempo of music provides stimuli to speed or slow walking cadences that are imperceptible to the patient. If successful, RAS/RAST-guided exercise programs will have far reaching implications not only for COPD and COVID 19, but for rehab in other chronic diseases including interstitial lung disease, cystic fibrosis, pulmonary hypertension, cardiomyopathies and peripheral arterial disease.^{19,20} If, as expected, our RAST music guided exercise program is successful, the result will also begin to finally address a critical knowledge gap on instituting music enhanced physical rehabilitation for patients recovering from COVID 19 symptoms.

A.3 Current Status of Research in this Area

A.3.1 Exercise Limitation in COPD. In patients with COPD, abnormalities in ventilatory, cardiovascular, locomotor, and neurosensory systems contribute to exercise limitation.²⁸ As COPD progresses, ventilatory and mechanical limitations to exercise become more prominent.^{28,29} The following sections are focused overviews of current knowledge on the impact of these factors on exercise capacity in COPD.

A.3.1.1 Exercise Limitation in COPD: Dynamic Hyperinflation and Respiratory Muscles. During whole body exercise, most patients with COPD experience an increase in end-expiratory lung volume (EELV).^{4,30,31} This increase results from expiratory flow limitation³² and tachypnea.³¹ The result is a progressive increase in end-inspiratory lung volume with an attendant decrease in inspiratory reserve volume (IRV).^{30,33} As we³⁰ and others have demonstrated,³³ critical decreases in IRV elicit unsustainable dyspnea, and patients stop exercising. Unsustainable dyspnea occurs because the critical decrease in IRV is accompanied by progressive neuromechanical uncoupling between respiratory muscle effort and size of tidal volume.²⁹

[figure not shown]

Fig 1. Rhythmic auditory stimulation (RAS) is achieved by embedding sonic enhancements in an instrumental track at fixed intervals, so that patients synchronize movements to the sonic enhancements.

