patients. The exercise physiologists, will assist with follow-up exercise, and will ask patients standardized questions regarding dyspnea, angina and ability to continue exercising.⁹⁸ She will be blinded to group assignment. The project manager ([name]) and exercise physiologist ([name]) and the statistician ([name]) will be aware of patient's group assignment.

Exercise Prescription. Upon randomization, all patients will receive a 1-hour educational session on exercise rehabilitation.

Specifically, the clinical exercise physiologist will work with patients to: (1) set up a schedule that fits with

Table. 4 Testing schedule

	Measure(s)	Screen/ Baseline	6- wks	12- wks	24- wks
Eligibility/Screening					
• FEV ₁ ≤ 70% FEV ₁ /FVC <70%	Pulmonary function test	x			
• Eligibility	History, Mini-Mental test	x			
• Co-morbidities	Charlson Index	x			
• Demographics	Demographic data information	x			
• Usual/leisurely walking cadence	Leisurely-paced 6MWT	x			
Primary Dependent Variable					
• Walking distance	Standard 6MWT	x x	x	x	x
Secondary Dependent Variables and Independent Variables					
• Dyspnea onset • Exercise duration (Treadmill walking time)	Constant-load treadmill test	x x	x	x x	x x
• QoL, Dyspnea, Self- efficacy, Physical Function	Questionnaires (SF-36, CRQ, Self-efficacy for walking) COVID 19 CAS	x	x	x	x
• Adherence	Fitbit Step Counts	x	x	x	x
• Daily physical activity	Step counts	x	x	x	x

Definition of abbreviations: 6MWT = six minutes walk test; QoL = quality of life

the patients' schedule for home-based exercise by with his/her usual daily schedule; (2) identify time-slots for exercise; (3) provide information on exercise tips; (4) address perceived barriers to exercise, (5) provide contact information, and (6) build a relationship with patients to provide support and identify health concerns.

C.1.6.1 Exercise Prescription:RAS/RAST-music group

C.1.6.1.a. Music selection: *Immediately after randomization, COPD patients in the RAS-music group will be asked to list 15 songs/music pieces within the one or more genres they most enjoy. If patients need help naming songs/music pieces, we will present them with a catalogue of "Top Twenty" songs/music within several genres. Patients will be also informed that they can choose songs/music not listed in the catalogue.*

COVID 19 patients in the RAST music group will meet with a music therapist at baseline and other timelines to complete their music assessment and music choices.

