C.1.8. Time Summary. The two groups of patients will complete the same testing procedures at the same time intervals. In Tab. 5, we summarize the timeline for completion of the proposed research project.

C.1.9. Measures:

Table. 5 COPD Timeline for research completion															
	Year 1				Year 2				Year 3				Year 4		
Finalize data collection instruments/ Purchase supplies	x														
Screen and enroll patients	x	x	x	x	x	x	x	x	x	x	x	x	x	x	
Train and follow patients		x	x	x	x	x	x	x	x	x	x	x	x	x	x
Data entry/Coding/Cleaning	x	x	x	x	x	x	x	x	x	x	x	x	x	x	x
Quality monitoring				x				x				x			
Data analysis/Preparation reports								x				x		x	x
Presentations/Publications (presentations at AACVPR, ACSM, ATS, Chest)								x			x		x	x	x

Definition of abbreviations: AACVPR = American Association of Cardiovascular & Pulmonary Rehabilitation; ACSM = American College of Sports Medicine; ATS = American Thoracic Society

COVID 19 timeline

Table 3. Timeline for research completion															
	Year 1				Year 2				Year 3				Year 4		
Finalize data collection instruments/ Purchase supplies	x														
Screen and enroll patients	x	x	x	x	x	x	x	x							
Train and follow patients	x	x	x	x	x	x	x	x							
Data entry/Coding/Cleaning	x	x	x	x	x	x	x	x							
Quality monitoring				x				x				x			
Data analysis/Preparation reports								x				x			
Presentations/Publications (presentations at AACVPR, ACSM, ATS, Chest)								x			x		x	x	x

Definition of abbreviations: AACVPR = American Association of Cardiovascular & Pulmonary Rehabilitation; ACSM = American College of Sports Medicine; ATS = American Thoracic Society

C.1.9.1. Six-minute Walk Tests (6MWT): Patients will perform two 6MWT as fast as they can without running according to ATS recommendations (standard 6MWT)⁹⁷ and two modified 6MWT at their usual/leisurely walk pace (*leisurely-paced 6MWT*). Walking cadence during these tests will be used to adjust the RAS exercise prescription (RAS-music group). In addition, data from the *standard 6MWTs* will be used to test the primary hypothesis that exercise training with RAS-music elicits greater increases in *standard 6MWT* distance than exercise training alone. Please note that the *leisurely-paced 6MWT* are only completed at baseline. The *standard 6MWT* are repeated at all testing time points (baseline, 6 weeks, 12 weeks and 24 weeks).

C.1.9.1.a. Standard 6MWT: Patients will be instructed to walk back-and-forth a 100-foot long circuit as

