C.1.9.5. Questionnaires: Self-reported physical function and quality of life will be evaluated using eight questionnaires (see **C.1.9.5.a. to C.1.9.5.e.**).

C.1.9.5.a. Chronic Respiratory Disease Questionnaire (CRQ). This questionnaire is designed to determine how the lives of patients with chronic airflow limitation are affected by the illness and the perceived impact of symptoms and limitations on quality of life.¹¹² Test-retest reliability and validity of the CRQ are well established.¹¹² Patients will not be informed of their previous responses on the questionnaire when the CRQ is administered at week 6 and 12 and 24. CRQ scores will be used as covariates in the final analysis if appropriate (see **C.2 Statistical Analysis**).

C.1.9.5.b. Short Form-36 Health Survey (SF-36): This is a general health-related quality of life

instrument to quantify perceived physical function and mental health.⁸ The SF-36 will be used to describe the sample and to have a comparator measure to published clinical pulmonary rehabilitation programs.¹¹³

C.1.9.5.c. Charlson Comorbidity Index. This validated¹¹⁴ and widely utilized index^{80,82} will be used to determine whether comorbidities influence study outcomes (see **C.2 Statistical Analysis**).

C.1.9.5.d. Depression and Anxiety. To control for the influence of ongoing depression and anxiety on adherence, the Center for Epidemiologic Studies Depression Scale (CES-D)¹¹⁵ and the State-Trait Anxiety Inventory (STAI)¹¹⁶ will be administered at baseline and at major data collection time-periods. CES-D and STAI scores will be used as covariates in the final analysis as appropriate.

C.1.9.5.e. Self-Efficacy. The Self-Efficacy for Walking¹¹⁷ and the Self-Efficacy for Shortness of Breath questionnaires¹¹⁸ will be used to measure self-efficacy at all time periods.¹¹⁷ These are reliable and valid¹¹⁸ instruments designed to assess a patient's confidence in keeping shortness of breath from interfering from walking or from doing what they want to do.

C.1.9.5.f. COPD Assessment Test The COPD Assessment Test (CAT) measures the impact COPD has on patient's well-being and daily life.

C.1.9.5.g Coronavirus Anxiety Scale (CAS) Assesses dysfunctional anxiety associated with the COVID19

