Three, limited adherence to home-based exercise: please see point One, *section C.4.2.*

C.4.4. Miscellaneous limitations and alternative methods

C.4.4.1. Medications: Medications may be adjusted throughout the study; such adjustments may affect outcome variables including exercise endurance. *Proposed Action:* Patients must be on stable therapy before enrollment. From our previous experience, we expect that several patients will require minor adjustments of their anti-hypertensive medication throughout the study. Medication lists and doses will be documented at each evaluation period. If patients require significant medication changes as judged by Drs. [name] (Pulmonary) or [name] (Data Safety Monitoring), appropriate statistical adjustments will be made.

C.4.4.2. Patients withdrawal: Patients may withdraw from the study at a higher rate than anticipated. *Proposed Action:* Since we use intent-to-treat analysis, any patient completing at least six weeks of training will be included in the analysis. If more than 20% of patients withdraw - or have to be withdrawn - prior to the sixth week of training, we will increase the number of randomized patients accordingly.

C.4.4.3. Lack of internet access: Some patients have no internet access. (Patients need internet access to sync the Fitbit). *Proposed Action:* Patients without internet access will be provided with a list neighborhood locations with Wi-Fi hotspots. Alternatively, patients will be free to come to the lab to sync

the Fitbit.

C.4.4.4. Music in the control group: Some patients in the control group may be used to listening to music while walking. *Proposed Action: Through the study, patients in the no-music group will be instructed to avoid listening to any music while walking.* In addition, at the end of the study, we will ask patients in the control group whether they listened to music while walking. Appropriate statistical adjustments will be made if needed.

C.5. Potential Problems.

C5.1. Insufficient patient enrollment. This is a very unlikely considering the large number of patients with COPD cared for at Hines VAH and our excellent track record.^{3,4,80,94} In addition, we could enroll patients from the Jesse Brown VA located 10 miles east of Hines. We could advertise in local newspapers and on Chicago Transit Authority busses.⁹⁶

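### COVID Objective 4 (exploratory) asks how music preference and history affect response with and without RAST music, but a music assessment is described only for the RAST arm, so only a within-RAST association can be estimated

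*Combined protocol and SAP*

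**What the plan says.** In A1 (COVID Patients), Objective 4 is labelled exploratory. Among the influences it sets out to examine are "clinical factors including those related to music preference and history on responsiveness to rehabilitation achieved with and without concurrent use of RAST music programs". The list of specific factors that follows again names "music preference and history". The COPD version of Objective 4 has no music factor.

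The only music assessment described is in C.1.6.1.a, within the exercise prescription for the music group: "COVID 19 patients in the RAST music group will meet with a music therapist at baseline and other timelines to complete their music assessment".

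For COVID controls:

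- Baseline testing in C.1.5, the no-music prescription in C.1.6.2 and the Usual Care Group paragraph describe no music assessment.
- C.1.9.5 opens with "Self-reported physical function and quality of life will be evaluated using eight questionnaires" and goes on to name CRQ, SF-36, Charlson, CES-D, STAI, two self-efficacy scales, CAT and CAS. None concerns music.
- In the questionnaire row of Table 4 ("Questionnaires (SF-36, CRQ, Self-efficacy for walking) COVID 19 CAS"), the COVID-specific entry is the CAS.
- C.4.4.4 states that "at the end of the study, we will ask patients in the control group whether they listened to music while walking".

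C.2.3 describes a linear regression and a mixed model with assigned group and the physiological, psychological and clinical factors as independent variables. Its factor list follows the COPD objective. It names no music factor and no interaction between group and factor.

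**The concern.** The objective has two halves: whether music background predicts gain when patients train with RAST music, and whether it predicts gain when they do not. The comparison of the two is what would make the result informative. If patients with a strong music background gain more in the RAST arm, that could mean they respond better to music, or that they would have improved more in any programme. Only the same measurement in controls can separate these.

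There is a secondary risk. C.2.3 enters the factors together. If a music factor recorded in one arm were added to that joint model and fitted to complete cases, the whole control arm would drop out, and with it the group term and the between-arm information on every other factor in the model.

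**Working it through.** The documents give no figure for Objective 4, so there is nothing to reproduce. The check is whether the quantities asked for can be estimated, and how precisely.

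**Inputs.** C.1.3 plans complete data on 72 COVID patients, 36 per group. By the text, the music factor is recorded in the RAST arm only.

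**Model.** Let G = 1 for RAST and 0 for control, and M = music factor:

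gain = b0 + b1·G + b2·M + b3·G·M

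Here b2 is the slope without RAST music, b2 + b3 the slope with it, and b3 the contrast.

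**Identifiability** (rank of the design matrix, 36 per arm):

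| Situation | Rank | What is lost |
|---|---|---|
| M in RAST only, complete cases (n = 36), interaction model | 2 of 4 | Group term, control slope, contrast |
| M in RAST only, complete cases, main effects only | 2 of 3 | Group term |
| M filled with a constant c in controls, interaction model | 3 of 4 | Control slope, contrast |
| M observed in both arms (n = 72) | 4 of 4 | Nothing |

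In the first two rows G equals 1 for every patient kept, so it duplicates the intercept, and G·M duplicates M. In the third row G·M = M − c·(1 − G), an exact combination of the other columns. Imputing M for controls would have to borrow its relation to gain from the RAST arm, which assumes away the difference in question.

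**What remains as written.** For a within-RAST correlation near zero with n = 36, the Fisher z half-width is 1.96/√(36 − 3) = 1.96/5.745 = 0.341. Back on the r scale, tanh(0.341) ≈ 0.33.

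**After the fix.** Assume 36 per arm, 80% power, two-sided 0.05, a normal approximation, a standardised covariate and residual SD 1. The multiplier is 1.960 + 0.842 = 2.802.

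- Control-arm slope: 2.802/√36 = 0.47 residual SD per covariate SD.
- Difference in slopes: 2.802·√(2/36) = 0.66.
- 50/50 binary factor (18 per cell), effect within controls: 2.802·√(2/18) = 0.93 SD.
- 50/50 binary factor, interaction: 2.802·√(4/18) = 1.32 SD.

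Collecting the form is not enough by itself. With main effects only, as C.2.3 stands, data from both arms yield one pooled slope, so the interaction term is needed too.

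**The case against.** The strongest reply is that little hangs on this. The objective is exploratory, the C.2.3 heading carries a note that it is not reported, and music is one item in a factor list. That stands and limits the weight of the point.

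A second reply is that absence from the documents does not prove absence from the study. Table 4 is not a full inventory: it also omits CES-D, STAI and CAT, which C.1.9.5 does describe. C.1.8 says "The two groups of patients will complete the same testing procedures at the same time intervals", and C.1.12 refers to an operations manual not included here. This stands in part. A reader might infer that control data are missing by design, but the documents support only that no assessment of controls is described. The C.1.8 sentence does not fill the gap, because the music assessment belongs to the RAST prescription and is not a listed test. The C.4.4.4 question checks for contamination at the end of the study and measures neither preference nor history.

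Three other stronger readings are not supported. First, a reader might conclude that the planned analysis will discard the control arm; C.2.3 names no music factor and states no complete-case rule, so this is a risk only if the factor is added to the joint model. Second, a reader might hold that RAST patients' answers are biased by knowing their assignment. Assessment after assignment is likely, since the sentence refers to patients already in that arm and C.1.5 places randomisation after baseline testing. But the COVID text says only baseline and other timelines, and the phrase placing music selection immediately after randomisation concerns COPD patients. Third, a reader might assume that the therapist's assessment captures music history; the text does not say so.

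Finally, the sponsor may have meant the music factors to apply only where music is used. That reading is possible, but the objective's wording covers both conditions and would need amending.

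**Conclusion.** The point holds in this limited form. On the plan as written, the music part of COVID Objective 4 reduces to a within-RAST association in about 36 patients (95% confidence interval about ±0.33 for r near zero), with no comparator. The control-arm slope and the between-arm contrast are not identified, and a larger sample would not change that. This assumes that the therapist meeting yields a usable preference and history measure and that no control assessment exists outside these documents.

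The primary 6MWT comparison does not use the factor. The other Objective 4 factors are untouched as long as the music factor is kept out of a joint complete-case model with them. The remedy makes the question estimable but not precise: a detectable slope difference of about 0.66 residual SD per covariate SD, on assumed rather than documented inputs. It is a cheap improvement to an exploratory objective, not a threat to the trial's main conclusion.

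**What to change.** Give every COVID patient the same short self-completed music preference and history form with the baseline questionnaires, before randomisation. Add it to Table 4 and C.1.9.5. The therapist can then use the RAST patients' forms when building playlists.

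In C.2.3, add the music factors for the COVID cohort and fit group, factor and group-by-factor in both arms, separately from the joint model for the other factors. Report slopes and their difference as exploratory, with confidence intervals, and say that only large interactions would be detectable.

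The cost is one form and a few lines of text, with no extra visit or staff if a short self-completed form is adequate; the documents name no instrument, so one must be chosen. The downsides are a few minutes of patient time and that controls are asked about music before being told to avoid it while walking. Baseline answers from before randomisation cannot be recovered later.

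If the form is not added, reword Objective 4 so that its music part is a within-RAST description only.

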During the **personalized RAS/RAST-music visit**, patients will complete one or more RAS-enhanced music cycles (i.e., warm-up, overload, and recovery) until the Research Assistant determines that the patient is comfortable with the procedure and successfully entrains his/her walking cadence with the music's tempo. (During the **personalized RAS/RAST-music visit**, patient and research staff will concurrently listen to the music so that the research staff may give real-time music-cadence entrainment feedback to the patient).

To avoid undue burden to patients with frequent return visits to the lab, the research staff will upload in the patients' smartphone or iPod four additional playlists each with approximately 15 songs. The music's tempo in these playlists will match the required increase in walk cadence as patients progress with training -- i.e., as the weeks pass, patients will be instructed by phone to move from one playlist to the next.

During the **personalized RAS/RAST-music visit**, patients will be instructed on the exercise prescription for the upcoming 12 weeks of exercise training. Specifically, patients will be instructed to walk while listening at the RAS-enhanced music at least 30 minutes, at least three times weekly. Compatible with perceived dyspnea (modified Borg < 3/10 [moderate dyspnea]),^{3,23} patients will be encouraged to extend the period of exercise by 5 minutes every 2 weeks (not to exceed 45 minutes)²³ (Patients will be notified that the 30-to-45 minutes of three- weekly exercise session can be achieved all in one bout of exercise or in more than one bout of exercise during the exercise day). Patients will also be asked to wear the Fitbit at all times except when showering.

At the conclusion of the **personalized RAS/RAST-music visit**, patients will be coached during 30-minutes of walking exercise to ensure that they properly understand how to conduct the RAS-music walking exercise at home and how to gauge dyspnea using the modified Borg scale.

At the end of weeks 2 and 4, 8 and 10, patients will be instructed by telephone to move to a new playlist in which RAS ensures a music tempo that is about 5% faster than in the preceding two weeks.⁹⁹ This step-up in the tempo of the RAS-enhanced music will take place only as long as dyspnea's Borg score is ≤ 3 at the conclusion of the prescribed walking exercise (modified from [name] et al).³ Frequency and duration of exercise will be the same as described above.

At week 6, patients will return to the lab and will repeat a *standard 6MWT* to calibrate the tempo of the RAS- enhanced music that he/she will use for the following 6 weeks of training (same as **personalized RAS/RAST-music visit** above). At week 12, patients will return to the lab (same steps as in week 6). The purpose of this 12-week visit is to recalibrate once more the tempo of the RAS-enhanced music so that if the patient is interested in using the RAS-music during the last 12 weeks of the study he/she may do so with an updated prescription of music. At weeks 6, 12 and 24 patients will also fill out questionnaires and complete the 7-day actigraphy. At week 12 and 24, patients will also undergo a quadriceps ultrasound and Quad-Tw testing (week 12 only).

During the **personalized RAS/RAST-music visit** and subsequent visits to the lab, the research staff will also ensure that patients know how to use the Fitbit, will reinforce on how to use RAS-enhanced music to guide the walking cadence and will inform patients that any time during the study they can obtain different songs if they do not like or get bored with the songs provided in their personal playlist.

C.1.6.2. Exercise Prescription: No-music group. One week after randomization, patients in the no-music group will return to the lab to receive detailed instructions about the 12-week no-music exercise walking program. Specifically, they will be instructed to exercise at least 30 minutes, at least three times weekly. The exercise will consist of repeated bouts of walking, which will be slow initially for about two minutes (warm-up phase – leisurely- paced walk), then fast as they can without running for about four minutes (same as *standard 6MWT*)⁹⁷ and then slow again for about one minute (recovery phase – leisurely-paced walk). Compatible with perceived dyspnea (modified Borg $< 3/10$ [moderate dyspnea])^{3,23} patients will be encouraged to extend the period of exercise by 5 minutes every 2 weeks (not to exceed 45 minutes).²³ (Patients will be notified that the 30-to-45 minutes of three- weekly exercise session can be achieved all in one bout of exercise or in more than one bout of exercise during the exercise day). Patients will also be asked to wear the Fitbit at all times except when showering. To conclude the visit, patients will be coached during a 30-minute walking exercise to ensure that they understood how to conduct the no-music walking exercise at home and how to gauge dyspnea using the modified Borg scale.

Of importance, the difference in exercise training between the no-music group and the RAS-music group is that the no-music exercise program **will not** be directed by RAS/RAST-enhanced music. *In addition, patients in the no-music group will be instructed to avoid listening to any music while walking.* All other methods, including phone calls at the end of weeks 2 and 4, 8 and 10 to ensure compliance and progression with home exercise, lab visits at weeks 6, 12 and 24 and encouragement to remain physically active after the first 12 weeks of training, will be same for both groups. (Patients will be scheduled so that the RAS-music and the no-music groups are not in the laboratory at the same time.)

COVID 19 Exercise and Strength Training (music and no music group)

Three times a week, patients will complete a muscle resistance/strength training session using professional grade resistance bands with handles (DYNAPRO™). Patients will complete upper, lower, and core body exercises. Training will include 9-11 exercises (e.g., shoulder press, lateral arm raises), will be progressive (i.e., bands with greater resistance will be used as participants' strength increases), and will be completed in two sets of 12-15 repetitions per exercise. Lower body exercises will include calf raises, chair sit to stands, and wall squats or squats with the resistance band. Core exercises will include basic planking exercises and abdominal work. Patients will record that they completed the strength training on their exercise log. We will focus on both upper, lower, and core body strength exercise as patients recovering from COVID 19 have generalized overall body weakness.

Usual Care Group: One week after randomization, patients in the control group will return to the lab to receive educational material on physical activity and general advice based on the 2018, *Physical Activity Guidelines for Americans* 2nd edition (U.S. Department of HHS) (see Appendix 4).¹⁴² Three times a week, patients will complete a muscle resistance/strength training session using professional grade resistance bands with handles (DYNAPRO™) (same as RAS-therapeutic music group).

C.1.7. Promoting & Assessing Adherence to the Exercise Program with and without RAS/RAST-music. To promote and monitor adherence to exercise (with or without RAS-music), all patients will be provided with a 3- axis accelerometer (Fitbit).¹⁰⁰⁻¹⁰² Patients will be instructed to download (sync) data from the Fitbit into their smartphone or iPod devices. These data will be saved in the associated online “Fitbit user account” set up by the study staff. During the 12-week period of exercise training, study staff will call patients on a weekly basis to go over daily and weekly walking data saved in the Fitbit account and to answer any questions that may arise. *To enhance/ensure compliance, our study staff will take a positive approach using motivational interviewing techniques.* After week 12, weekly phone calls will stop. To maintain engagement with study staff, patients will be called again at week 18. At week 23, they will be called to be reminded of the final visit that will take place on week 24.

C.1.8. Time Summary. The two groups of patients will complete the same testing procedures at the same time intervals. In Tab. 5, we summarize the timeline for completion of the proposed research project.

C.1.9. Measures:

Table. 5 COPD Timeline for research completion															
	Year 1				Year 2				Year 3				Year 4		
Finalize data collection instruments/ Purchase supplies	x														
Screen and enroll patients	x	x	x	x	x	x	x	x	x	x	x	x	x	x	
Train and follow patients		x	x	x	x	x	x	x	x	x	x	x	x	x	x
Data entry/Coding/Cleaning	x	x	x	x	x	x	x	x	x	x	x	x	x	x	x
Quality monitoring				x				x				x			
Data analysis/Preparation reports								x				x		x	x
Presentations/Publications (presentations at AACVPR, ACSM, ATS, Chest)								x			x		x	x	x

Definition of abbreviations: AACVPR = American Association of Cardiovascular & Pulmonary Rehabilitation; ACSM = American College of Sports Medicine; ATS = American Thoracic Society

COVID 19 timeline

Table 3. Timeline for research completion															
	Year 1				Year 2				Year 3				Year 4		
Finalize data collection instruments/ Purchase supplies	x														
Screen and enroll patients	x	x	x	x	x	x	x	x							
Train and follow patients	x	x	x	x	x	x	x	x							
Data entry/Coding/Cleaning	x	x	x	x	x	x	x	x							
Quality monitoring				x				x				x			
Data analysis/Preparation reports								x				x			
Presentations/Publications (presentations at AACVPR, ACSM, ATS, Chest)								x			x		x	x	x

Definition of abbreviations: AACVPR = American Association of Cardiovascular & Pulmonary Rehabilitation; ACSM = American College of Sports Medicine; ATS = American Thoracic Society

C.1.9.1. Six-minute Walk Tests (6MWT): Patients will perform two 6MWT as fast as they can without running according to ATS recommendations (standard 6MWT)⁹⁷ and two modified 6MWT at their usual/leisurely walk pace (*leisurely-paced 6MWT*). Walking cadence during these tests will be used to adjust the RAS exercise prescription (RAS-music group). In addition, data from the *standard 6MWTs* will be used to test the primary hypothesis that exercise training with RAS-music elicits greater increases in *standard 6MWT* distance than exercise training alone. Please note that the *leisurely-paced 6MWT* are only completed at baseline. The *standard 6MWT* are repeated at all testing time points (baseline, 6 weeks, 12 weeks and 24 weeks).

C.1.9.1.a. Standard 6MWT: Patients will be instructed to walk back-and-forth a 100-foot long circuit as

fast as they can without running.⁹⁷ Standardized encouragement will be given.⁹⁷ Heart rate and blood pressure will be monitored to ensure safety. The entire test will be recorded with a camcorder to count the number of steps and, thus, calculate patient's cadence for the overload phase of RAS training (modified from Ho et al.⁵⁸ and Liu et al.¹¹).

C.1.9.1b Leisurely-paced 6MWT: The purpose for this test is to identify the patient's leisurely walking cadence to set the music tempo during the warm-up and cool-down phases of the home-based exercise (RAS- music group). The test will be identical to the *standard 6MWT* with the exception that patients will be instructed to walk at their usual leisurely walking pace. We chose six minutes of observation because, in older adults, a one-minute step-count can overestimate usual walking cadence by as much as 40%.¹⁰³ The entire test will be recorded with a camcorder to count the number of steps and, thus, calculate patient's cadence for the warm-up and cool-down phases of RAS training (modified from Ho et al.⁵⁸ and Liu et al.¹¹).

C.1.9.2 Standard 6MWT testing has been used to assess therapeutic responses in patients with COPD. This test has the potential to produce complementary information about changes in exercise performance following interventions. Accordingly, we are including this test for the following reasons: (1) The *standard 6MWT* is more reflective of activities of daily living than other walk tests and is currently the test of choice when using a functional walk test for clinical or research purposes;⁹⁷ and (2) The *standard 6MWT* assesses the submaximal level of functional capacity. Most patients limit their own intensity of exercise and are allowed to stop and rest during the test. Because most activities of daily living are performed at submaximal levels of exertion, the *standard 6MWT* may better reflect the functional exercise level for daily physical activities;⁹⁷ (3) The *standard 6MWT* has a defined clinically important difference;⁹⁷

C.1.9.3. Actigraphy: Daily physical activity will be quantified using a lightweight (27 gm.), small (3.8 x 3.7 x 1.8 cm), triaxial accelerometer worn on the hip (actigraph GXT3). The actigraph GXT3 detects accelerations ranging from 0.05 to 2.5 Gs and it has a frequency responses ranging from 0.25 to 2.5 Hz. Motion outside human movements are rejected by a bandpass filter. The acceleration/deceleration signals are digitized by an analog - to-digital converter at 30 times/second (30 Hz) over a pre-programed epoch interval. The monitor is programmed for start time and data collection interval, and data are retrieved for analysis. The device is capable of recording up to 22 days of continuous data in one-minute epochs. The actigraph GXT3 is both reliable (Intraclass Correlation Coefficient (ICC) for activity counts of 0.97)¹⁰⁴ and valid in measuring physical activity¹⁰⁵ even in patients with low levels of overall physical activity.¹⁰⁶ Since physical activity is known to vary based on the day of the week due to work and leisure activities profiles,¹⁰⁷ patients will be instructed to wear the sensor for 8 days, 24 hours a day.¹⁰⁸ At the end of day-8, patients will doff and mail the Actigraph to the lab.

C.1.9.4. Fitbit Step Count: The Fitbit is a commercially-available motion sensor (3-axis accelerometer) designed to monitor number of steps taken, activity (sedentary, light activity, moderate activity, moderately vigorous), distance walked and sleep.³⁰ Specific Fitbit devices can be worn at the hip, pocket and wrists.¹⁰⁹ The Fitbit device worn at the waist is highly accurate in step counting¹⁰¹ – i.e., high correlation with observed step counts ($r=0.97$ to 0.99)¹⁰¹ and high ICC (0.97).¹¹¹ Fitbits worn at the wrist are not as accurate as those worn at the hip^{101,111} – the Fitbit worn on the wrist can underestimate step counts by 16% for slow walking and by 11% for moderately fast walking.¹⁰¹ Relevant to our proposal, however, is the fact that most patients are very receptive to wear wristband Fitbits for long periods of time.¹⁰⁹ Accordingly, we will use the wristband Fitbit as a source of general information on daily level of physical activity during the 12 weeks of exercise training and will use that information to monitor adherence to the program and to motivate patients to exercise. We will use hip actigraph recordings¹⁰⁰ to accurately quantify physical activity (see **C.1.9.3.**).

